### Event-free Survival (EFS) for AML

Event-free survival is defined as the interval from the first dose of IP to the earlier date of induction treatment failure, relapse for those who have induction treatment success (e.g., complete remission), or death due to any cause. Censoring is at the last evaluable

post-baseline response assessment; otherwise, at the first dose of IP. The event date for induction treatment failure is assigned as the date of the first dose of IP.

EFS time in months: (event date - first dose of IP date +1)/30.4

Overall Response Rate (ORR)

ORR is the incidence of either PR or better based on investigator assessment. All subjects that do not meet the criteria for response (PR or better) by the analysis cutoff date will be considered as non-responders.

**For MM subjects: The earliest record where PR or better response has to be confirmed by two consecutive same/better response assessments at any time and should be on/before new anticancer therapy start date. sCR, CR, VGPR and PR are considered as PR or better responses.**

**For AML subjects: The earliest record where PR or better response collected does not need to be confirmed by subsequent assessment and should be on/before new anticancer therapy start date. CRMRD-, CR, CRi(CR with incomplete hematologic recovery), MLFS and PR are considered as PR or better responses.**

Overall survival (OS)

OS is defined as the time from first dose of IP date until death due to any cause.

OS time in months: (date of death - first dose of IP date +1)/30.4

Subjects without event will be censored at their last date known to be alive.

Progression-free survival (PFS) for MM

PFS time is calculated as time from first dose of IP date to disease progression date or death due to any cause, whichever is earlier.

PFS time in months: (event date - first dose of IP date +1)/30.4

Subjects without disease progression or death until the analysis data cut-off date will be censored at the last **non-missing evaluable** disease assessment date. **Subject will be censored at last non-NE post-baseline disease assessment before any anti-cancer therapy. If there are no post-baseline disease assessment, then subjects are censored at treatment start date.**

Time to Response (TTR)

Time to response is defined as the time from the first dose of IP until the first documentation of response (PR or better). Only subjects who have achieved a response will be evaluated for TTR.

TTR time in months: (date of the first observation of response - first dose of IP date +1)/30.

### **Dose intensity**

**Dose intensity indicates actual dose (mg) given per cycle, which is the cumulative dose divided by the number of cycles started.**

### **Relative Dose intensity**

**Relative dose intensity is calculated as actual cumulative dose / planned cumulative dose, where**

- **Actual cumulative dose [mg] is defined as the total dose given during the study treatment exposure till the course of study. For subjects who did not take any drug the actual cumulative dose is 0 mg.**
- **Planned cumulative dose [mg] is defined as the per-protocol planned dose accumulated over the actual duration on study treatment, whether the actual visit is missing or not.**

## **6. Analysis Sets**

### **6.1 Full Analysis Set**

The FAS is defined as all subjects that are enrolled and receive at least 1 dose of AMG 176.

### **6.2 Safety Analysis Set**

**The Safety Analysis Set is same as the Full Analysis Set as described in Section 6.1.**

### **6.3 Per Protocol Analysis Set(s)**

Not applicable.

### **6.4 Health-related Quality-of-Life or Health Economics Analyses Set(s)**

Not applicable.

### **6.5 Pharmacokinetic Analyses Set(s)**

The pharmacokinetic analysis set is defined as all subjects who have received at least 1 dose of AMG 176 and for whom PK parameters can be adequately estimated. These

subjects will be evaluated for PK analysis unless the number of data points required for analysis is not enough, or significant protocol deviations have affected the data, or if key dosing or sampling information is missing.

#### **6.6           Interim Analyses Set(s)**

Not applicable.

#### **6.7           Study-specific Analysis Set(s)**

##### **6.7.1       Interim Efficacy Analysis Set**

**Interim Efficacy Analysis Set is a subset of the Full Analysis Set (FAS) and it includes subjects whose data cut-off date is at least 4 weeks after the first dose date.**

##### **6.7.2       DLT Evaluatable Analysis Set**

A subject is deemed DLT evaluable if during the DLT observation period the subject met at least one of the following criteria:

- received at least 75% of the planned dose of AMG 176 (and 100% of the planned doses of azacitidine in Part 4) and completed the DLT observation period
- experienced a DLT

### **7.           Planned Analyses**

#### **7.1       Interim Analysis and Early Stopping Guidelines**

No formal interim efficacy analysis is planned for this study. **Interim safety analyses will be performed to support the evaluation of safety by the DLRT.** However, safety data will be reviewed on an ongoing basis. The Dose Level Review Team (DLRT) will review all available cumulative data by cohort prior to making dose escalation decisions. Adverse events and DLTs observed in all subjects will be evaluated continually and considered in all enrollment and dosing decisions.

**Additional interim analyses will be performed when the target number of subjects enrolled in each part has had the opportunity to complete 6 months of treatment.**

#### **7.2       Primary Analysis**

A primary analysis will occur when the last subject has had opportunity to complete 6 cycles of the treatment of AMG 176.

#### **7.3       Final Analysis**

A final analysis is planned after all subjects have had the opportunity to complete the last study visit.

If FA is close to PA then FA will be performed.

#### **8. Data Screening and Acceptance**

##### **8.1 General Principles**

The objective of the data screening is to assess the quantity, quality, and statistical characteristics of the data relative to the requirements of the planned analyses.

##### **8.2 Data Handling and Electronic Transfer of Data**

The Amgen Global Study Operations-Data Management (GSO-DM) department will receive and store all data to be used in the planned analyses. This study will use the RAVE database.

##### **8.3 Handling of Missing and Incomplete Data**

The following imputation for missing or incomplete data will be performed if required:

Incomplete adverse event and concomitant medication dates missing data will be imputed as described in [Appendix A](#).

Non-pharmacokinetic measurements (eg. biomarker data) that are above or below the quantification limits will be considered equal to the upper or lower limit of quantification for all analyses unless specified otherwise.

##### **8.4 Detection of Bias**

Lack of protocol compliance and the potential for biased statistical analyses will be examined by assessing the incidence of important protocol deviations in each cohort. The clinical study team will identify and document the criteria for important protocol deviations.

##### **8.5 Outliers**

Outlier data will not be excluded unless scientifically justified.

PK concentration data will be evaluated for outliers by visual inspection and decisions to re-assay individual samples will be made in accordance with standard Pharmacokinetics and Drug Metabolism (PKDM) practices.

##### **8.6 Distributional Characteristics**

Where appropriate, the assumptions underlying the proposed statistical methodologies will be assessed. If required data transformations or alternative non-parametric methods of analyses will be utilized.

### **8.7 Validation of Statistical Analyses**

Programs will be developed and maintained, and output will be verified in accordance with current risk-based quality control procedures.

Datasets, tables, figures, and listings will be produced and validated in accordance with SOP-430399. Standard macros will be used when available.

The production environment for statistical analyses consists of Amgen-supported versions of statistical analysis software; for example, the SAS System version 9.2 or later.

## **9. Statistical Methods of Analysis**

### **9.1 General Considerations**

Descriptive statistics on continuous data will include means, medians, standard deviations and ranges, while categorical data will be summarized using frequency counts and percentages. Graphical summaries of the data may also be presented.

When data are summarized by time, the values recorded against the scheduled time points listed in the protocol will be used. When assessing minimum/maximum increases or decreases over the study, all assessments, including unscheduled assessments will be used.

For each indication, efficacy and safety data will be summarized by dose level.

For the subjects who complete the DLT period and proceed to a higher dose level or crossover to a combinational therapy cohort for the following treatment cycle, efficacy and safety will be analyzed by the initial assigned dose level.

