9.3 Analysis Sets, Subgroups, and Covariates

9.3.1 Analysis Sets

The analysis of all endpoints (see Section 3), unless noted otherwise, will be conducted on the Full Analysis Set (FAS), and by cohort. The FAS is defined as all subjects that are enrolled and receive at least 1 dose of AMG 176. The analysis of DLT will be restricted to DLT evaluable subjects (see Section 6.2.1.2.1). The PK Analysis Set will contain all subjects who have received at least 1 dose of the investigational product and have at least 1 PK sample collected. These subjects will be evaluated for PK analysis unless the number of data points required for analysis is not enough, or significant protocol deviations have affected the data, or if key dosing or sampling information is missing.

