9.4.2 Methods of Analyses

9.4.2.1 General Considerations

Descriptive statistics will be provided for selected demographics, safety, PK, PD and ██████████ by dose, dose schedule, and time as appropriate. Descriptive statistics on continuous data will include means, medians, standard deviations and ranges, while categorical data will be summarized using frequency counts and percentages. Graphical summaries of the data may also be presented. Unless otherwise specified, statistical analyses will be done using the FAS, which includes subjects that are enrolled and received at least 1 dose of AMG 176. Data will be analyzed by dose level for each part.

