**Exploratory analysis will be performed separately if needed.**

### **9.2 Subject Accountability**

The number and percent of subjects who are enrolled, receive investigational product, completed investigational product, discontinue from investigational product (including reasons for discontinuation), complete study, discontinue the study (including reasons for discontinuation) will be summarized by cohort. Enrollment by country and study site will be summarized.

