### 9.6.2 Adverse Events

The Medical Dictionary for Regulatory Activities (MedDRA) version **26.1** or later will be used to code all events categorized as adverse events or disease related events to a

system organ class and a preferred term. The severity of each adverse event will be graded using CTCAE version 4.0.

Subject incidence of all treatment-emergent adverse events, serious adverse events (SAEs), grade 3 or higher, treatment-related, serious treatment-related, adverse events leading to withdrawal of investigational product, and fatal adverse events will be tabulated by system organ class and preferred term by dose level. The event categories of adverse event and disease related event both will be included.

For subjects who experienced COVID-19, SAEs on or after COVID-19 onset will be summarized.

Subject incidence of DLTs will be summarized by preferred term and dose level using the DLT Evaluatable Analysis Set. **Summary table may not be generated if the number of events is less than 5 in each cohort. The individual subject-level data will be provided.** Similar summaries will also be provided to events of interest. A listing of death will be provided.

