#### 9.6.6        **Electrocardiogram**

All on-study ECG data including PR, QRS, QT, RR, QTcB, and QTcF interval will be summarized **for AML parts only. Mean  $\pm$  SE by visit graph may be plotted for QTcF and QTcB.**

Summaries over time and/or changes from baseline over time will be provided for all ECG parameters.

Subjects will be categorized into the following groups per their maximum change from baseline in QTcF. Unscheduled assessments will be included in the determination of the maximum change.

- $\leq$ 30 msec
- >30 – 60 msec
- >60 msec

The number and percentage of subjects in each group will be summarized.

Subjects will also be categorized into the following groups per their maximum post baseline QTcF. Unscheduled assessments will be included in the determination of the maximum post baseline value.

- $\leq$ 450 msec
- >450 – 480 msec
- >480 – 500 msec
- >500 msec

The number of subjects in each group will be summarized for each dosing group.

In addition, the relationship between PK concentration of AMG 176 and change from baseline in QTcF may be explored graphically **and performed by clinical pharmacology modeling and simulation (CPMS) team.**

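### SAP 9.1 groups efficacy and safety by dose level within indication; the protocol's part, schedule and cohort are lost and section 10 does not declare it

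*SAP*

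**What the plan says.** SAP 9.1 gives the general rule: "For each indication, efficacy and safety data will be summarized by dose level". For subjects who move to a higher dose or cross over to the combination, the same section says that "efficacy and safety will be analyzed by the initial assigned dose level". It names neither the initial part nor the initial cohort.

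Later SAP sections repeat this unit. In 9.6.2 adverse event incidences "will be tabulated by system organ class and preferred term by dose level", and DLTs are also summarised by dose level. In 9.6.3 the laboratory shift tables use dose level. The ORR entry in 9.5.2 (Table 3) names the Full Analysis Set but no grouping, so 9.1 is its only rule. Other sections use other units. Disposition in 9.2 "will be summarized by cohort", and for the QTcF categories 9.6.6 says: "The number of subjects in each group will be summarized for each dosing group".

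The protocol is finer. Section 9.3.1 says that the analysis of endpoints, unless noted otherwise, "will be conducted on the Full Analysis Set (FAS), and by cohort". Section 9.4.2.1 calls for descriptive statistics "by dose, dose schedule, and time as appropriate" and adds: "Data will be analyzed by dose level for each part". Section 9.4.2.3.1 frames the primary DLT analysis part by part, and 9.4.2.3.3 tabulates laboratory shifts by cohort.

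SAP section 10 lists analyses that will not be done because the study ended early. It does not mention grouping.

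**The concern.** In this study a dose in mg/m² does not identify a treatment. The same number was given once or twice weekly, alone, with azacitidine or with itraconazole, depending on the part. The primary objectives (SAP 2.1) are tied to regimen: an MTD for BIW in Part 1a, for QW in Part 1b and for BIW in Part 3a, and an MTCD only for the combination in Part 4.

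If a programmer builds table columns from 9.1 as worded, each DLT, adverse event or response rate becomes an average over regimens, weighted by how many subjects each happened to enrol. That number answers none of these objectives. Because the study ended early, only a synopsis report with selected analyses is planned, and PFS, EFS and TTR are dropped. The adverse event, DLT and ORR tables therefore carry most of what will be reported.

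**Working it through.** The plan states no figure to reproduce here. The check compares the two rules and counts what each would merge.

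**1. Inputs.** Regimens come from the design tables (SAP 3.1, Protocol Table 4-1) and the Part 5A doses (120 and 240 mg/m²) from Protocol 4.1.1. Whether anyone enrolled in Part 5 is not shown, so Part 5 is kept in a separate column.

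| AML dose (mg/m²) | Groups sharing one row under SAP 9.1 | Without Part 5 | With Part 5 |
|---|---|---|---|
| 60 | 3a BIW mono; 3d QW with itraconazole in week 1; Part 4 QW + azacitidine | 3 | 3 |
| 120 | 3a BIW mono; 3b QW mono; 3c QW mono; Part 4 QW + azacitidine; cohort 5a BIW + azacitidine; [one Part 5A cohort] | 5 | 6 |
| 180 | 3a BIW mono; 3b QW mono; Part 4 QW + azacitidine | 3 | 3 |
| 240 | 3b QW mono; Part 4 QW + azacitidine; cohort 5b BIW + azacitidine; [one Part 5A cohort; Part 5B Regimens 1 and 2] | 3 | 6 |
| Total | | 14 | 18 |

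**2. Number of rows under each rule, AML.**
- Indication × dose (SAP 9.1): 4.
- Part × dose: 3 (3a) + 3 (3b) + 1 (3c) + 1 (3d) + 4 (Part 4) = 12 without Part 5; adding 2 (5A) + 1 (5B) gives 15.
- Part × schedule or regimen × dose: 14 without Part 5, 18 with it.

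Part × dose still merges Part 4 QW with BIW at 120 and at 240 (14 − 12 = 2). Separating them needs the protocol's reference to schedule or to cohort.

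**3. The same for myeloma.** Part 1a has 6 doses listed before the ramp-up entry and 4 with ramp-up; Part 1b has 4. That makes 6 + 4 + 4 = 14 groups. The distinct doses are 30, 40, 50, 60, 120, 180, 240, 360 and 480, so SAP 9.1 gives 9 rows. Part × dose gives 9 + 4 = 13. The 240 mg/m² row under SAP 9.1 holds Part 1a without ramp-up, Part 1a with ramp-up and Part 1b QW.

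**4. What a merged row mixes.** Protocol 6.1.1 gives 4 AMG 176 doses per cycle for QW and 6 for BIW. At 120 mg/m², where no ramp-up applies, that is 4 × 120 = 480 against 6 × 120 = 720 mg/m² per cycle, with and without azacitidine.

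**5. Illustration only.** From Protocol Table 2-1, responses of PR or better:
- 120 mg/m²: BIW mono 1/5 (20.0%), QW mono 0/5, QW + azacitidine 1/4 (25.0%). Pooled: (1 + 0 + 1)/(5 + 5 + 4) = 2/14 = 14.3%, exact 95% CI 1.8 to 42.8.
- 240 mg/m²: QW mono 1/4 (25.0%), QW + azacitidine 2/6 (33.3%). Pooled: 3/10 = 30.0%, exact 95% CI 6.7 to 65.2.

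The 2/14 is not the full 120 mg/m² row. It omits cohort 5a, which has no data in the documents, and Part 3c, for which Protocol 4.3.3 reports 0 of 4 with CR or CRi; adding Part 3c gives 2/18 = 11.1%. The column labels of Table 2-1 are also uncertain as they read: the Part 3b monotherapy columns sum to 5 + 5 + 4 = 14, against 11 enrolled. With so few subjects the figures show no difference between regimens. They show only that the pooled rate belongs to none of them.

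**The case against.** The strongest reply is that dose level is loose shorthand for dose cohort. SAP 3.3 writes dose level where the matching sentence in Protocol 4.1.1 writes dose cohort. SAP 9.6.2 tabulates DLTs by dose level but sets its threshold for omitting the table per cohort. The crossover sentence in 9.1 does most work if it means the assigned cohort, since a subject can move from monotherapy to the combination at the same mg/m². SAP section 1 also says that the SAP details analyses already outlined in the protocol. This much stands: a reader might infer that the SAP plans to pool regimens, and the documents do not support that. Pooling is the literal result of the wording and is nowhere announced. Shorthand does not settle the matter, however, because 9.1 names a stratum, and that stratum is the indication where the protocol has the part.

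A second reply also stands. No formal hypothesis is tested (SAP 2.2), and dose decisions are made by the DLRT under the mTPI rule at the current dose (SAP 3.3 and 7.1). A reader might infer that the MTD or MTCD determination is compromised; nothing in the documents supports that.

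A third reply is that restoring the protocol's phrase about parts would not be enough. That is correct, as step 2 of the working shows for Part 4. It bears on how the fix is worded and does not remove the discrepancy.

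**Conclusion.** The point holds as an undeclared and ambiguous departure from the protocol's unit of analysis, in the rule that governs the primary safety tables and ORR. Taken literally, it reduces 14 AML groups to 4 rows (18 to 4 if Part 5 enrolled) and 14 myeloma groups to 9. The SAP's mix of dose level, cohort and dosing group leaves the table columns undefined. It is a should-fix correction of reporting and has no bearing on DLRT dose decisions.

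Two limits apply. Mixing ramp-up with no ramp-up is not a general problem: it arises only for myeloma Part 1a at 240 mg/m², because every AML target of 180 mg/m² or more uses ramp-up. The Part 1a split itself rests on reading the two listings of 240 mg/m² in the design tables as two separate groups. Counts that include Part 5 assume enrolment that the documents do not show.

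**What to change.** In SAP 9.1, state that efficacy and safety are summarised by part, schedule or regimen (QW, BIW, Regimen 1, Regimen 2) and dose cohort, with Part 1a 240 mg/m² with and without ramp-up in separate columns. State that subjects who escalate or cross over are analysed under their initial part and cohort. Use the same unit in 9.5.2, 9.6.2 and 9.6.3, and define the dosing group of 9.6.6 as that unit. If a pooled column is wanted, show it beside the regimen columns and list it in section 10 with the reason.

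The cost is SAP wording and column definitions; no new data are needed. The tables become wider and many cells small, which the SAP already allows for by giving subject-level data where DLT or time-to-event counts are low.

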**Exploratory analysis will be performed separately if needed.**

### **9.2 Subject Accountability**

The number and percent of subjects who are enrolled, receive investigational product, completed investigational product, discontinue from investigational product (including reasons for discontinuation), complete study, discontinue the study (including reasons for discontinuation) will be summarized by cohort. Enrollment by country and study site will be summarized.

### **9.3 Important Protocol Deviations**

Important Protocol Deviations (IPDs) categories are defined by the study team before the first subject visit and updated during the IPD reviews throughout the study prior to database lock. These definitions of IPD categories, sub-category codes and descriptions

will be used during the course of the study. Eligibility deviations are defined in the protocol. IPDs and eligibility deviation will be summarized. A listing will be provided for IPD.

#### **9.4 Demographic and Baseline Characteristics**

The following descriptive summaries of the demographic and baseline characteristics will be produced: Demographic (i.e., age, age groups [18 to < 65, 65 to < 75, 75 to < 85, ≥ 85 years], sex, race, and ethnicity) and baseline characteristics (height, weight, disease type/sub-type, prior lines of therapy, and ECOG Performance Status, Multigated Acquisition (MUGA) Scan or Echocardiogram, Neurological Status) will be summarized using descriptive statistics. If multiple races have been reported for a subject, the subject will be categorized as multiple.

## 9.5 Efficacy Analyses

### 9.5.1 Analyses of Primary Efficacy Endpoint(s)/Estimand(s)

Not Applicable.

### 9.5.2 Analyses of Secondary Efficacy Endpoint(s)/Estimand(s)

Table 3. Efficacy Endpoint Summary

Endpoint	Statistical Analysis Methods
ORR	The proportion of subjects with response (PR or better) with corresponding 2-sided exact 95% CI will be calculated using the Clopper-Pearson method ( Clopper and Pearson, 1934 ) for the Full Analysis Set. Refer Appendix C for code fragment.
DOR, PFS (for MM) and EFS (for AML)	Kaplan-Meier estimates and Kaplan-Meier curve will be provided for the Full Analysis Set.
TTR	Descriptive statistics will be provided for subjects with response.

For time to event endpoints (including DOR, TTR, EFS and PFS), summary table or figure may not be generated if the number of events is less than 10. The individual subject-level data will be provided.

